the CLC in a month per person year at risk of hospitalization in that month. This measure has been constructed per CLC using VHA-Medicare merged data from 2004 and afterwards obtained under [name] current HSR&D IIR. The measure will be constructed covering the period from at least the 24 months preceding the introduction of the INTERACT program until 24 months after the introduction of the INTERACT program. Since hospitalization rates vary substantially during flu season, we have fit an ARIMA model to reduce the heterogeneity of variance in this monthly measure of hospitalization, thereby reducing the heterogeneity of residual variance. An ARIMA model will be fit for each CLC in the study, then using the monthly difference between the observed to the expected value to compare between any two matched CLCs over time. The dependent measure is a facility aggregate which we will risk adjust using indirect standardization by stratifying the per CLC month measure separately for long stay and short stay person months at risk of hospitalization. [See the Statistical Considerations section below for a detailed presentation of the ARIMA model.]

[figure not shown]

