We will test the effect of INTERACT on the rate of hospitalization from CLCs taking advantage of *both* the paired control CLCs as well as the differences in the hospitalization rates among intervention facilities before and after the implementation of the intervention. The primary outcome variable is the monthly rate of hospitalization, which, after adjusting for seasonality and trends in the rate over several years prior to the intervention, is compared to the rate of the paired comparison CLC. To allow for regional differences in seasonality, separate ARIMA models will be run for each CLC and then we will use the monthly difference between the observed to the expected CLC hospitalization rate value to compare between the two matched CLCs, aggregating these differences overall pairs. Technically, the average monthly rate of hospitalization before the intervention will be compared to the average monthly rate after and the difference between these two rates will be compared to the differences in the rates of the comparison facilities, using a standard *difference in difference* design.

A similar approach will be used with the person level, risk adjusted hospitalization rates for short and long stay residents calibrated as an annualized rate and there will be fewer facility years than were facility months under the approach described above. The unit of analysis will be the CLC resident but the standard errors will be clustered at the facility level.

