Using the results of the Structured Implicit Review process, we will determine the percent of hospital transfers rated as avoidable through better quality of preventive care and early change recognition and the percent rated as inappropriate because the Veteran’s condition could have been safely managed in an average VA CLC. We will compare the percentage hospitalized before the implementation to that after implementation. The sample size of 326 hospitalization records, 163 pre and 163 post-INTERACT, is based upon the assumption that the pre-intervention rate of potentially avoidable hospitalizations will be 40%. For the overall project, we are hypothesizing that there will be a 20% reduction in hospitalizations. Logically, the reductions in hospitalizations will come primarily from the "avoidable" type (otherwise we have a causal inconsistency). Thus, if 40 of 100 hospitalizations pre INTERACT are avoidable and all of the 20% reduction in hospitalizations (20 of 100) will come from among those that are avoidable, we expect a 50% reduction in the rate of avoidable hospitalizations. So, if the pre rate is 40% and the post rate is 20%, using a one tailed test at the alpha .05 level, we need about 100 records

before and 100 after to achieve a power of .90. In the event that some "unavoidable" hospitalizations are really avoided due to the intervention, we increase the sample size to 163 per time period.

Finally, we will test for unintended consequences by examining changes in the rates of overall mortality and in the rate of decline in the late loss ADLs, as measured by the MDS 3.0 nursing home resident assessment, which is done upon admission, periodically thereafter and upon discharge.[45]

Random selection of records with a transfer: A total of 326 medical records with a transfer to the hospital and across the eight intervention CLC sites will be reviewed, 163 pre-INTERACT intervention and 163 post-intervention.

The 163 pre-INTERACT records will be selected from a list of transfers that occurred during the 18 months prior to INTERACT being introduced to the CLCs. This list will be compiled by the study programmer/analysts who will pull it from current CDW data and MDS data. Once the list is generated, random selection will occur to obtain 163 records pre-intervention.

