We estimate our power to detect an expected decrease in hospitalization rate over a 24 month period using simulation analysis, over different scenarios with different sample sizes (# of CLCs), to predict the expected power of our pair matched experiment. Previous research reveals that a Auto-Regressive Moving Average (ARIMA) model characterizes hospitalization rate trends with high accuracy. In our simulations analysis we assume that each CLC’s rate follows an ARMA(2,2) model of the following form:

$$Y_t = c + \epsilon_t + \sum_{i=1}^2 \rho_i Y_{t-i} + \sum_{i=1}^2 \theta_i \epsilon_{t-i}$$
, where ρ_i the correlation of the current to the previous i months, θ_i is the parameter that describe the effect of the error at time $t-1$ on the current hospitalization rate, ϵ_t is normal random with mean zero and standard deviation of σ_ϵ and c is the overall expected hospitalization rate. The simulation analysis included 5 parameters: 1) the sample size in the treatment group; 2) an increase/decrease in the hospitalization rate variance σ_ϵ (F); 3) the size of the effect (c); 4) the accuracy of the decrease $\sigma_{c.}$; and, 5) the variability of ρ_i , θ_i of the nursing home that received treatment from the matched nursing home that received control σ_d . For each configuration of the five parameters, the following algorithm was repeated for 100 times: 1. a sample of n yearly hospitalization rates was chosen from currently observed empirical hospitalization rates and assigned to treatment and control CLCs; 2. sample ρ_i 's, θ_i 's from the above ARMA(2,2) model randomly generated for each of n treatment CLCs; 3. for each i treated nursing home we perturbed the ρ_i 's, θ_i 's by a factor of σ_d , and assigned them to the pair matched control CLC; 4. generate $2n$ ARMA processes using the ρ_i 's, θ_i 's generated in step 2 and 3, and the variance σ_ϵ/F ; 5. decrease the hospitalization rate in the treated group gradually by 5c% to 20c% over 24 months + random deviation of σ_c ; 6. calculate the monthly differences between the treated nursing home hospitalization rate to its matched control, and average across 24 months (τ_j) and calculate the standard error σ_{τ_j} ; and finally, 7. use the average and variance

$$\frac{\sum_{j=1}^J \frac{\tau_j}{\sigma_{\tau_j}}}{\sum_{j=1}^J \frac{1}{\sigma_{\tau_j}}} \text{ and its pooled variance } \left(\sum_{j=1}^J \frac{1}{\sigma_{\tau_j}^2} \right)^{-1}$$

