calculated in 6 to obtain overall weighted average and its pooled variance. To find the factors with the largest effect on power, we calculated the MSE of all the main effects and their interactions. The F, n and c are factors that capture 93% of the variability in the data. Figure 1 shows how the # of CLCs and F (variance of hospitalization rate) affect the power of our analysis. . Even if the monthly reduction in hospital rate will be as low as 10%, using 8 treatment CLCs will result in .77% power.

Figure 4: Power Estimates, Number of CLC’s by Effect Size and Variance in Monthly Hospitalization Rates

Effect	20% Reduction in Hosp. Rate	10% Reduction in Hosp. Rate
--------	-----------------------------	-----------------------------

size										
# CLCs	6	7	8	9	10	6	7	8	9	10
.5	1	1	1	1	1	.99	1	1	1	1
1.0	.98	.99	.99	1	1	.7	.74	.77	.81	.84

Preliminary Studies:

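### The printed power (.77 at 10%, .99 at 20%, 8 CLCs) was simulated for a post-period-only contrast, not for the planned pre/post difference-in-difference, whose standard error, alpha and sidedness are not stated

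*Combined protocol and SAP*

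**What the plan says.** **Simulated contrast.** In Statistical Considerations, step 5 of the simulation lowers the treated rate over 24 months. Step 6 is to "calculate the monthly differences between the treated nursing home hospitalization rate to its matched control, and average across 24 months", with a standard error for each pair. Step 7 uses the quantities "calculated in 6 to obtain overall weighted average and its pooled variance". The pooled variance printed there is the inverse of the sum of 1/σ_τj² over pairs. Each configuration had few replicates: "the following algorithm was repeated for 100 times".

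**Result.** In the power table (captioned Figure 4), variance row 1.0 gives .77 for a 10% reduction and .99 for 20% with 8 CLCs. The text repeats the first: "using 8 treatment CLCs will result in .77% power" (read here as .77). It adds: "The F, n and c are factors that capture 93% of the variability in the data".

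**Planned analysis.** Under Aim #4, "the average monthly rate of hospitalization before the intervention will be compared to the average monthly rate after", and that change is compared with the change in the matched controls. A separate ARIMA model per CLC supplies expected values. Study Procedures (Overview) sets two years before and two years after. Outcome Measures builds the rate "from at least the 24 months preceding the introduction of the INTERACT program". The CLC is the randomised unit (Patient Selection).

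**Not stated.** No standard error, degrees of freedom, alpha or sidedness is given for this facility-level test. The phrase "using a one tailed test at the alpha .05 level" belongs to the chart-review sample size. The clustered standard errors under Aim #4 belong to the resident-level alternate outcome.

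**The concern.** A reader will take .77 and .99 as the power of the primary test. The difference-in-difference carries the noise of the pre-period mean, or equivalently the error in the ARIMA-expected value. The simulated contrast carries neither.

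The simulated data do vary between pairs (σ_c in step 5, σ_d in step 3), but the test variance in step 7 uses only each pair's own monthly error.

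The hypothesised effect is a 20% reduction, and there the printed .99 suggests almost no risk of a missed effect. Separately, with no stated standard error or alpha, the variance of the primary test could be chosen after the data are seen.

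**Working it through.** **1. Can the printed figure be reproduced?** Not directly. Values for σ_ε, the ARMA coefficients, σ_c, σ_d, alpha and sidedness are not printed. A consistency check is possible: solve the noncentrality (ncp) that gives .77 at n = 8, then scale it by √(n/8).

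- Two-sided .05: ncp = 1.960 + .739 = 2.699.
- One-sided .05: ncp = 1.645 + .739 = 2.384.

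| CLCs | 6 | 7 | 8 | 9 | 10 |
|---|---|---|---|---|---|
| Printed, 10%, row 1.0 | .70 | .74 | .77 | .81 | .84 |
| Two-sided z | .647 | .714 | .770 | .817 | .855 |
| One-sided z | .663 | .721 | .770 | .812 | .846 |

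With 100 replicates the Monte Carlo standard error at .77 is √(.77 × .23/100) = 4.2 points (exact 95% interval .68 to .85). The table fits either sidedness and cannot show which was used.

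**2. Loss from the contrast alone (z-test).** Assumptions: 8 pairs, alpha .05, independent months, equal variance before and after, no added between-pair variance, printed values correct for the simulated contrast. The variance ratio of the difference-in-difference to the post-only mean is (1/24 + 1/m)/(1/24) = 1 + 24/m for m pre-months. This is 2 for m = 24 and 1.4 for an assumed m = 60. The ncp is divided by the square root of the ratio.

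At 20%, the printed .99 gives ncp = 1.960 + 2.326 = 4.286 two-sided, or 1.645 + 2.326 = 3.971 one-sided.

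Example, 10%, m = 24, two-sided: 2.699/√2 = 1.908, and Φ(1.908 − 1.960) = .48.

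**3. Further loss with a pair-level t on 7 df.** This test is proposed here; the plan does not state it. The same ncp goes into the noncentral t distribution.

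| Two-sided (one-sided) | z, m = 24 | z, m = 60 | t, m = 24 | t, m = 60 |
|---|---|---|---|---|
| 10%, from .77 | .48 (.52) | .63 (.64) | .38 (.45) | .50 (.57) |
| 20%, from .99 | .86 (.88) | .95 (.96) | .74 (.81) | .87 (.91) |
| 20%, ncp twice the 10% value | .97 (.96) | 1.00 (.99) | .90 (.92) | .97 (.97) |

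The two 20% rows differ because the anchor is uncertain. Taken as 99 of 100 replicates, .99 has a 95% interval of .946 to .9997. Doubling the 10% ncp implies .997 and .999 two-sided at 6 and 7 CLCs, where the table prints .98 and .99.

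**4. More pairs.** With 15 pairs the ncp is multiplied by √(15/8) and the t has 14 df. With 24 pre-months this gives .68 (.71) at 10% and .97 (.98) at 20%, anchored on .99.

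**5. Why the missing between-pair term matters.** If between-pair variance is R times the within-pair variance, a nominal two-sided .05 z-test that ignores it rejects under the null with probability 2[1 − Φ(1.96/√(1 + R))]. That is .08 for R = .25 and .26 for R = 2. R is an assumption; the documents give no value.

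**The case against.** **The 93% statement.** Statistical Considerations reports that F, n and c account for nearly all the variation, so σ_c and σ_d moved the simulated power little. This stands as a description of what drove that simulation. It does not put a pre-period or a between-pair variance into the test that was simulated.

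**A reader might infer that the simulated test is more lenient than the planned one.** The documents do not support this, because no planned test is stated to compare it with. The step from .48 to .38 at 10% is likewise a loss against a test proposed here, not against the plan. The printed step 7 is also loose: it weights by 1/σ but gives the variance that belongs to 1/σ² weights, so the exact test variance is uncertain.

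**Twenty-four pre-months is the harshest reading.** Outcome Measures says at least 24, and Aim #4 speaks of several years of prior trend. The observed-minus-expected wording also brings the planned analysis closer to a post-period contrast. This stands: a longer pre-period shrinks the loss, as the 60-month column shows. The error in the expected value is still absent from the simulation.

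**Difference-in-difference does not always cost power.** It removes stable baseline gaps between pair members. In a simulation calibrated to .77 (mean rate 1.3 per person-year, no autocorrelation, assumed gap SD of 0.2), it had power .38 against .26 for a valid post-only pair-level t-test at 10%. This stands. Step 1 appears to give both pair members one rate, though its wording does not settle the matter.

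**Timing.** The version is dated 06/28/2017, and the project timeline places training in 4/15-8/15 and analysis in 4/17-8/17. Restating power cannot change the sample. Fixing the test before the outcome analysis still has value.

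**Conclusion.** The mismatch holds and needs no assumption: the printed powers belong to a different contrast from the planned one, and the primary test's standard error, alpha and sidedness are unspecified. Confidence in this is high.

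Confidence in the size is low. Under the assumptions above, the contrast alone takes 8 pairs to between .48 and .64 at 10% and, anchored on .99, between .86 and .96 at 20%. The pair-level t figures are a separate, further step.

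The results apply to variance row 1.0 only; row .5 prints power 1 for 8 CLCs at 10%. A reader might infer that the printed figures are arithmetically wrong, or that the trial is underpowered for its hypothesised 20% effect. The documents show neither: the simulation's inputs are not printed, and the 20% result ranges from .74 to above .99 with the test, the anchor and the pre-period. This should be fixed.

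**What to change.** Before the outcome analysis, state the primary test at the level of randomisation: one ARIMA-adjusted (observed minus expected) difference-in-difference per pair, tested by a paired t on J − 1 df or an exact sign-flip test. With 8 pairs the smallest two-sided sign-flip p-value is 2/2⁸ = 2/256 = .008, so that test remains usable. Give alpha, sidedness and the pre-period length.

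Re-run the simulation with that contrast and that test, using several thousand repetitions. Report σ_c, σ_d and F. Restate power for 8 to 15 pairs at 10% and 20%, showing the loss from the contrast and from the test separately.

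The cost is SAP wording and computing time, with no new sites or data. The downside is that the stated power will probably fall; a longer pre-period would reduce the fall.

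### Step 7 of the power simulation weights the pairs by 1/SE but takes its variance from weights 1/SE², so the printed standard error is too small whenever pair SEs differ

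*Combined protocol and SAP*

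**What the plan says.** Under Statistical Considerations, step 6 takes the monthly treated-minus-control differences within each pair, with the instruction to "average across 24 months (τ_j) and calculate the standard error σ_{τ_j". So σ_j is a standard error, not a variance. Step 7 ("and finally, 7. use the average and variance") then prints two formulas over the J pairs:

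- pooled mean = Σ(τ_j/σ_j) / Σ(1/σ_j)
- its pooled variance = [Σ(1/σ_j²)]⁻¹

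The text says the step 6 results are used "to obtain overall weighted average and its pooled variance", so the two formulas are meant to work together. The power table follows. For a 10% reduction the text says "using 8 treatment CLCs will result in .77% power"; the table shows .77, so this is a proportion and not a percentage. The same row gives .99 for 8 CLCs at a 20% reduction.

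Aim #4, which describes the primary analysis, compares observed with ARIMA-expected rates within pairs, "aggregating these differences overall pairs". It states no weights and no variance.

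**The concern.** The variance of a weighted mean depends on the weights. The printed variance is that of the inverse-variance weighted mean, which is the smallest variance any weighted mean of these pairs can have. Attaching it to a mean with other weights makes the standard error too small and the test statistic too large. A simulation that counts rejections this way rejects too often when there is no effect and reports more power than a valid test on the same estimator would have.

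The two formulas agree only when all σ_j are equal, and the simulation does not make them equal. Its ARMA coefficients are "randomly generated for each of n treatment CLCs" and then perturbed for the matched control, so precision varies from pair to pair.

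At stake are the stated power for the minimum number of sites and, if the formula is reused, the error rate of the primary test.

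**Working it through.** **The plan's own figure.** The .77 cannot be reproduced. For this simulation the plan gives no alpha or sidedness, no σ_ε, no ARMA coefficients, no σ_c or σ_d, and no empirical rates. The only alpha in the documents, one-tailed .05, is for the chart-review sample size in Aim #4. The check below therefore takes .77 as printed and asks how far the mismatch could move it.

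**Algebra.** For independent pairs with known σ_j and weights w_j, the variance of the weighted mean is Σ(w_j²σ_j²)/(Σw_j)².

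- With w_j = 1/σ_j (the printed weights): J/(Σ 1/σ_j)².
- With w_j = 1/σ_j²: 1/Σ(1/σ_j²), which is the printed variance.
- Ratio of true to printed variance: J·Σ(1/σ_j²)/(Σ 1/σ_j)² = 1 + CV²(1/σ_j), where CV is the coefficient of variation across pairs. By Cauchy-Schwarz this is at least 1, and it is 1 only if all σ_j are equal.

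**Small example.** Four pairs have SE 1 and four have SE 2.

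- Σ(1/σ) = 4 + 2 = 6 and Σ(1/σ²) = 4 + 1 = 5.
- Printed SE = √(1/5) = 0.447. Correct SE = √8/6 = 0.471.
- 400,000 random draws gave an SE of 0.471, and the printed rule rejected 6.3% of the time under no effect at two-sided .05.

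**Effect on the table.** Let r be the true SE divided by the printed SE, and z the critical value (1.96 for two-sided .05).

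- Actual two-sided error of the printed rule: 2·[1 − Φ(z/r)].
- If a tabulated power P came from the printed rule, power with the matching variance is Φ(Φ⁻¹(P) − z·(1 − 1/r)).
- Here Φ⁻¹(.77) = 0.739 and Φ⁻¹(.99) = 2.326.

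With J = 8 and σ_j evenly spaced on the log scale (assumed):

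| Range of σ_j | Σ(1/σ) | Σ(1/σ²) | Variance ratio | SE too small by | Actual error | .77 becomes | .99 becomes |
|---|---|---|---|---|---|---|---|
| 2-fold | 5.804 | 4.424 | 1.051 | 2.5% | 5.6% | .755 | .989 |
| 3-fold | 4.923 | 3.411 | 1.126 | 5.7% | 6.5% | .734 | .987 |
| 4-fold | 4.424 | 2.929 | 1.197 | 8.6% | 7.3% | .716 | .985 |

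The 3-fold row in full: 8 × 3.411/4.923² = 1.126, r = 1.061, and 0.739 − 1.96 × (1 − 1/1.061) = 0.626, so Φ = .734.

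**Sensitivity.**

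- At a 1.5-fold range the error is 5.2% and .77 becomes .765, which is negligible.
- With a one-sided .05 test, the 2- to 4-fold ranges give an error of 5.4% to 6.6% and .77 becomes .758 to .725.

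**Simulation noise.** With 100 replicates the Monte Carlo standard error at .77 is √(.77 × .23/100) = .042. The shifts of .015, .036 and .054 are about 0.4, 0.9 and 1.3 of these standard errors.

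**The case against.** Four points can be made for the plan.

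**The square may simply be missing from the text.** The printed variance is exactly right for 1/σ² weights. A slip by the authors or in converting the document would explain the mismatch and leave the power table intact. Conversion alone is less likely, because the square is absent from both numerator and denominator of the mean but present in the variance beside them. A typing slip remains plausible, so this point stands: any claim about the table depends on what was coded.

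**It hardly matters at the hypothesised effect.** The plan expects a 20% reduction, and there .99 stays at about .985 or more. Eight is the minimum number of sites, and up to 15 pairs are planned. This stands. At 10% the shift is also about the size of the simulation noise. But that noise can go either way and shrinks with more replicates, whereas this bias goes one way and does not.

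**The simulation does not model CLC size.** A reader might infer that the 3- or 4-fold rows follow from real differences between CLCs in size and hospitalization rate. They do not. The simulation uses a Gaussian process with one stated error scale, σ_ε/F, and no person-time enters it. The described source of unequal σ_j is the pair-specific coefficients, whose spread is not given. The table rows are illustrations, not corrected values.

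**The formula belongs to the simulation, not to the analysis.** A reader might infer that the trial's primary test will have an inflated error rate. The documents do not show that. Aim #4 describes a difference-in-difference comparison, does not refer to step 7 and gives no weights. Step 7 is, however, the only pooling formula in the plan, so an analyst could reuse it.

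**Conclusion.** The mismatch is in the text and its direction is certain: as printed, the standard error is never too large, and it is too small whenever pair SEs differ. Its size cannot be fixed from the documents. It rests on assumed values for alpha, sidedness and the spread of SEs, and on treating the σ_j as known and the pairs as independent.

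Under the assumptions shown, and if the printed formulas were coded, the overstatement of power is modest at a 10% reduction (about 1.5 to 5 points) and immaterial at 20%. The case for correcting it is that the formula is wrong as written and cheap to put right, not that the trial is seriously underpowered. An inflated error rate in the trial's own test is a risk only if step 7 is carried into Aim #4.

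**What to change.** 1. Confirm whether the simulation code used weights 1/σ_j or 1/σ_j².
2. Make the text consistent: either weights 1/σ_j² with variance 1/Σ(1/σ_j²), or weights 1/σ_j with variance J/(Σ 1/σ_j)².
3. If 1/σ_j was coded, rerun the simulation with a matched pair of formulas and restate the power table, with alpha and sidedness. If 1/σ_j² was coded, only the text changes.
4. If Aim #4 will pool pairs this way, state the same matched formulas there.

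The cost is one line of formula and, at most, a rerun of the simulation. Keeping 1/σ_j weights would lower the stated power as shown above. Moving to 1/σ_j² weights need not: under the same assumptions power is Φ(r × 0.739), about .776, .784 and .791 for the three ranges. No site, data collection or clinical procedure is affected.
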